6. STUDY PROCEDURES

Provide detailed description of all study visits, procedures, and data collections, including:

- **Description of each study visit and procedures at each visit (include a schedule/table of study procedures)**

Initial enrollment (~30 to 60 minutes total):

After the consent, our trained study clinician will administer the intervention to the participant in-person, on the phone, or over zoom depending on participant preference. After the intervention is completed, the RA will obtain post-enrollment questionnaires and also schedule dates/times for the follow-up appointments. With participants' permission, the study clinician will document the clinically important findings elicited from the participant (e.g., preferences for end-of-life care goals) in Epic's ACP module and also send an email regarding the findings to patient's outpatient clinicians within Mass General Brigham health system via secure email. The study team will also provide the post-enrollment patient handout (see attachment) to the participants. All participants in the intervention arm will receive the same intervention and follow-up procedures.

Follow-up appointments (~30 to 45 minutes each):

During the scheduled follow-up appointments on the phone/zoom, our RA will administer surveys to assess for the outcomes. In addition, if the participants report that they have not had conversations with their outpatient clinicians about ACP, our study clinician will conduct brief coaching to overcome the obstacles participants might be facing in this process and also document clinically relevant information in Epic to notify to the outpatient clinician.

Table 3 Study visits		
Study visit	Intervention	Outcome assessment
Initial enrollment	ED GOAL	Post-enrollment survey

1-month follow-up	ACP navigation coaching (as needed)	Follow-up patient-reported outcomes surveys
3-month follow-up	ACP navigation coaching (as needed)	Follow-up patient-reported outcomes surveys
6-month follow-up	ACP navigation coaching (as needed)	Follow-up patient-reported outcomes surveys

- **Description of study drugs, devices, or other interventions/exposures administered, including:**

- **Dose, method of administration, schedule of administration, dose modifications**

Our intervention is followed by scheduled, follow-up visits at one, three, and six months afterwards. The follow-up visits will be performed to assess the outcomes as well as to serve as the ACP care navigation/coaching by our study clinician.

Study clinician training:

We will train the study clinicians to administer these tools by 3-hour didactic on the concepts of delirium, cognitive impairment, and dementia, as well as bedside practice administration with the PI until competency is demonstrated (PI will self-record the responses next to the study clinician administering the instrument and compare the results. We will repeat this process with new patient volunteers until there is no discrepancy). In the case of equivocal findings on these assessments administered by study clinician, the PI backup will be available.

Intervention fidelity:

To ensure that all study clinicians deliver our intervention consistently, we will check the intervention fidelity. The percent adherence to the intervention fidelity checklist will be measured for every participant encounter (see attached fidelity checklist). High fidelity will be defined as mean adherence of >70% to the components on the fidelity checklist, which is consistent with expert consensus for behavioral intervention studies.²⁸

- **Justification and safety information if FDA approved drugs will be administered for non-FDA approved indications (“off-label”): How are doses, routes of administration, or participant populations different from FDA approved indicated use?**

Not applicable.

- **Description of specific data variables to be collected, including data collection methods, assessments, data collection sheets, and/or schedule of assessments (A schedule/table of study assessments is preferred)**

Measures	Descriptions	Timing
ACP engagement survey for patients (primary outcome)	Used for patients , this validated instrument will measure the self-reported processes for ACP (knowledge, contemplation, self-efficacy, and readiness), and ACP behavior. ²⁹	Baseline & at 1, 3, and 6 months
ACP engagement survey for caregivers (primary outcome)	Used for surrogate decision-makers , this ACP engagement survey is validated to measure the same ACP processes and behaviors. ³⁰	Baseline & at 1, 3, and 6 months
EMR documentation (primary outcome)	Review EMR to see if new documentation of ACP conversation, change in code status, or advance directive forms documented by physicians or mid-level providers exist.	Baseline & at 1, 6, and 12 months
Self-reported ACP conversation survey (primary outcome)	Quantitative and qualitative questionnaires to assess the self-reported completion of ACP conversations with outpatient clinicians and families as well as barriers/facilitators of this process.	At 1, 3, and 6 months

Heard and understood survey (secondary outcome)	A validated instrument for seriously ill patients to report how well they feel heard and understood about their wishes for end-of-life care. ³¹	Baseline & 1, 3, and 6 months
Quality of communication survey (secondary outcome)	A validated instrument to measure the quality of communication about end-of-life care. ³²	Baseline & at 1, 3, and 6 months
Healthcare utilization (secondary outcomes)	Review EMR to see # of urgent care visits, ED visits, hospitalizations, hospice visits, and outpatient visits.	At 6 and 12 months before and 1, 6, 12 months after enrollment
Mortality	Review EMR to determine patient's vital status.	At 1, 3, and 6 months
Qualitative benefits and obstacles of ACP conversations after ED GOAL (secondary outcome)	Semi-structured interviews to assess the benefits of ED GOAL and obstacles participants faced in completing more ACP conversations with their outpatient clinicians and loved ones after ED GOAL (see interview guide).	At 1, 3, and/or 6 months

- **Description of planned genetic research as applicable (e.g., specific description of whole genome sequencing, creation of immortalized cell lines or induced pluripotent stems cells, and sharing of genetic material with collaborators and central repositories as applicable, etc.)**
Not applicable.
- **Description of plans for return of research results as applicable (e.g., specific description of, rationale for, and process by which research results will be returned, including to whom, by whom, and when, etc.). Include plans for managing incidental findings as applicable.**
Not applicable.
- **Definition of primary and secondary outcomes/endpoints. Note that outcome measures should be quantifiable and measurable.**
Please see **Table 4** above.
- **Definition of study termination criteria, e.g., objective criteria for clinical worsening, lack of improvement, and/or unacceptable adverse events**
 - We do not anticipate any adverse events (AE) for this study other than loss of confidentiality. Any AE will be reported to our institutional review board at the time of annual continuing review by the principal investigator using an Adverse Event Form in accordance with the MGB Human Research Committee guidelines for AE reporting.
- **Local site restrictions or site-specific procedures as applicable, including:**
 - **Description of how study procedures (e.g. intervention or diagnosis) compare to standard of care, including description of alternative treatments, procedures, or methods of diagnosis**
There will be no study procedures.
 - **Description of what happens to participants receiving therapy when study ends or if a participant's participation in the study ends prematurely.**
Not applicable.
 - **For studies that are conducted entirely internationally, describe the nature of the involvement of investigators at each site in the study, i.e., indicate which personnel will be present at the international site(s) and describe the nature of their involvement, including which staff will have direct contact with subjects and/or**

perform any study related procedures and which staff will have access to study data and perform data analysis

There will be no transfer of data to an outside institution for this study.

- **Remuneration as applicable. Indicate if payments to subjects are made upon completion of study visits/certain procedures and how remuneration is pro-rated, particularly for non-completers**

We will provide remuneration of \$48 (gift card purchased through MGB approved mechanisms or check, depending on participant preference).

- **Description of plans for sending and/or receiving specimens or data with research collaborators outside Mass General Brigham or with NIH (e.g., dbGaP) or other tissue/data repositories (include details of identified versus de-identified sharing, how data or specimens are labeled/coded, secure transfer method, external IRB approval as applicable, storage for future use, secure transfer method, etc.)**

No transfer of data to an outside institution will be for this study.

7. Risks and Discomforts

Provide detailed description of potential risks of each study-related procedure/intervention, including:

- **Complications of surgical and non-surgical procedures**

Not applicable.

- **Drug side effects and toxicities**

Not applicable.

- **Device complications/malfunctions**

Not applicable.

- **Psychosocial risks**

The participants will be introduced or re-initiated on the topic of ACP. Some patients with serious illness do not wish to discuss ACP because they feel uncomfortable with the topic. This potential discomfort, however, is a part of the routine practice in the ED. Many ED clinicians discuss ACP with patients routinely, and the study does not add additional discomfort that is different from the routine clinical practice. Further, the PI is trained in serious illness communication and will be available to manage patients' anxiety and other emotions as needed.

- **Privacy/confidentiality risks**

Loss of confidentiality is a minor risk. The protection of data for this study includes the following:

1) Study data will be collected and managed using Dropbox Business, which is fully encrypted and is compliant with Partners' policies and procedures. Data pertinent to this study will only be given access to only the members of our study team approved by the IRB.

2) REDCap electronic data capture tools, which are hosted at BWH¹. REDCap (Research Electronic Data Capture) is a secure, web-based application designed to support data capture for research studies, thereby providing an intuitive interface for validated data entry, audit trails for tracking data manipulation and export procedures, automated export procedures for seamless data downloads to common statistical packages, and procedures for importing data from external sources.

3) Study participants will be identified by a unique numeric identification, and their protected health information (PHI) will be de-identified.

4) Study participant PHI will be collected and stored on a secure REDCap survey, which will be created on a secure, password protected desktop computer located at BWH where only the study staff will have access.

5) At study completion, contact information and the link between the identifying information and their data will be destroyed.

6) Finally, to ensure that all staff is compliant with confidentiality training, all study staff has completed the CITI course for the protection of human subjects training in research ethics and good clinical practice.

- **Genetic research risks**

Not applicable.

- **Radiation risks**

Not applicable.

- **Include description of steps taken to decrease relevant risks, including the following:**

- **How procedures used are consistent with sound research design and do not expose unnecessary risks**

Verbal consent will be obtained from the patient / caregiver participants. After learning about the general background of the study and reading the study information sheet (electronic or hardcopy), the potential participants will be able to decline to participate. Further, if the participant expressed anxiety or distress from the intervention (determined by the treating clinician), he/she is offered to discontinue the study and the PI will be responsible to care for the participant's emotional needs. The PI will also contact the patient's primary outpatient clinician to ensure adequate follow up of the patient after leaving the ED.

- **When appropriate, researchers use procedures already being performed on subjects for diagnostic or treatment purposes**

Not applicable.

8. Benefits

Provide detailed description of potential benefits of study participation, including:

- **Either describe potential benefits to participating individuals or clearly state that there is no direct benefit to individuals**

No definitive benefit has been demonstrated. However, our prior pre/post-intervention studies indicated that the intervention may lead to increased ACP engagement in patients with serious illness (see **Previous Studies** section above).

- **If multiple subject populations are to be enrolled, describe any differences between groups with regard to potential benefit (e.g. potential for benefit to an affected subject population versus no potential benefit for healthy controls, etc.)**

Based on the demographic data that we have thusfar, we do not anticipate differences between groups with regard to the potential benefit.

- **Potential benefits to society (e.g., increased understanding of disease process, etc.)**

For our patients, we hope that our intervention will lead patients to have more ACP conversations with their outpatient clinicians and loved ones. ACP conversations can lead to well-informed shared decision making and improved quality of life at the end of life.¹ For the society, ACP conversations are associated with lower rates of in-hospital death, less aggressive medical care at the end of life, earlier hospice referrals, increased peacefulness, and a 56% greater likelihood to have end-of-life wishes known and followed.¹⁻⁸ Furthermore, patients with documented ACP conversations experience a 36% reduction in the cost of end-of-life care, with an average cost savings of \$1,041 per patient in the last week of life.⁹

9. Statistical Analysis

Describe plans for statistical analysis, including:

- **Statistical methods/data analysis plan**

Aim 1 quantitative data analysis:

We will conduct an intention-to-treat analysis. Since the primary outcome is mean change in self-reported ACP engagement, we do not expect differences among patients who are admitted vs. discharged. For our secondary outcome, we suspect that there is a propensity of more ACP documentation in patients who are hospitalized and missingness in patients who are primarily cared for at outside institutions. We will plan to use regression in subgroup analysis for ACP documentation to account for hospitalization status. In addition, we will perform sensitivity analyses to account for clustering by individual outpatient clinicians, palliative care consultations, and cognitive impairment status. We will also perform sensitivity analyses for survey respondents (e.g., patients vs. caregivers). We will compare patient demographics by study arm to assess randomization using bivariable analyses (t-test for continuous variables and chi-square for categorical variables). The mean changes in ACP engagement (primary outcome) at one month will be compared by study arms to estimate effect sizes. Within arms, we will use a one-sample binomial exact test of proportions for categorical outcomes (e.g., EMR documentation), and Wilcoxon signed ranks test for ordinal outcomes (e.g., ACP Engagement Survey) at baseline, after the intervention at one month. A p-value of 0.05 will be the significance threshold. To address missing data, I will conduct a secondary analysis using linear mixed models at baseline and one month. For qualitative outcomes,

Aim 2 qualitative data analysis:

We will conduct in-depth, semi-structured interviews with participants. We will explore the perceived benefits of the intervention as well as barriers to completing ACP conversations after leaving the ED. The interviews will be recorded and professionally transcribed. The transcripts will be analyzed to identify recurring themes that illustrate the qualitative benefits (e.g., how the intervention changed their lives) and barriers to completing ACP conversations (e.g., how attempted ACP conversations were unsuccessful). Transcripts will be analyzed by two trained researchers to ensure interpretive integrity and consistency per standard comprehensive qualitative analysis methods. We will use framework analysis as the analytic approach,³³ which allows the flexibility of incorporating *a priori* considerations as well as more emergent themes in the data. The coding structure will be collaboratively and iteratively developed by the research team and include both prefigured and emergent codes.³⁴ We will use an ethnographic data management software program, NVivo 10 (QSR International). If there are disagreements, the mentors/advisors and we will review the quotes and themes to discuss their meaning and to achieve consensus. We will follow the consolidated criteria for reporting qualitative research.³⁵

- **Power analysis (e.g., sample size, evaluable subjects, etc.)**

For Aim 1 (quantitative data):

While this pilot RCT study is not powered to detect statistically significant differences in the ACP outcomes, we will compare 1-, 3-, 6-month ACP outcomes in the intervention arm to the control arm to estimate the preliminary effect sizes. Our prior study demonstrated a mean patient-reported ACP engagement increased from 3.8 to 4.3 on a 5-point scale, corresponding to a moderate effect size of 0.50.³⁶ A conservative estimate of effect size is 0.25. We also expect that 10% of enrolled patients will die before completing all follow-ups. With a sample size of 60 patients per group, we would have 90% power to detect the difference using a 2-sided Fisher's exact test ($\alpha=0.05$). We plan to exclude patients who die before 6-month in the analysis.

For Aim 2 (qualitative data):

Based on my previously successful study, in which I explored patients' attitudes about *ED GOAL*,³⁷ interviewing ~10 dyads of patients and caregivers (N~20 total) with a diverse representation of perspectives will yield thematic saturation for tailoring *ED GOAL*. However, I will continue to enroll more participants if thematic saturation is not achieved.

10. Monitoring and Quality Assurance

Describe the plans that will be followed by study staff for monitoring and quality assurance, including:

- **Adverse event criteria and reporting procedures**

Any AE will be reported to our institutional review board at the time of annual continuing review by the principal investigator using an Adverse Event Form in accordance with the Partners Human Research Committee guidelines for AE reporting.

- **Planned safety monitoring, e.g., data monitoring committee (DMC)/data and safety monitoring board (DSMB), independent monitor, PI-monitored, etc., including planned frequency of review. If DMC/DSMB monitored, include either charter as separate attachment or complete DMC/DSMB [APPENDIX](#)**

The proposed research is a minimal risk study and does not meet the criteria for an NIH-defined Phase III trial given no patient outcomes will be collected. Therefore, a data and safety monitoring board will not be required, and PI will be solely responsible for data and safety monitoring of the proposed research. In the event of an adverse event, the research team will report immediately to the PI, who will be responsible for management and reporting to the IRB, and to the NIH institute.

- **Outcomes monitoring, including planned frequency of review.**

Not applicable.

- **Study stopping rules as applicable**

Unanticipated Problems (UP): As with any AE above, the PI will report any UP within 5 working days / 7 calendar days of the date. The investigator first becomes aware of the problem using an Adverse Event Form in accordance with the Partners Human Research Committee guidelines for AE reporting Please see attached institutional policy.

- **Internal monitoring of source data, protocol adherence, and recordkeeping, including which staff will be responsible and planned frequency of review**

The PI is responsible for monitoring and recordkeeping on REDCap and qualitative interview findings.

- **Independent monitoring of source data as applicable**
All personal health information will be removed from the research data from the participants and clinicians at the earliest possible time. All data will be stored in a secured Partners approved shared drive accessible only to the study staff. Recordings will be stored on an encrypted recording device and saved to the secure Partners-approved shared drive.

11. Privacy and Confidentiality

- **Select the Privacy and Confidentiality measures that apply to this research by checking the box next to each statement (Check all that apply)**
 - **Note that not all of the measures outlined below may apply to your study**
 - **Do not delete statements that do not apply to your study; leave the boxes unchecked**
 - **Describe any additional privacy and/or confidentiality measures that are not captured by the check box items in free text following the check boxes**
-
- Study procedures will be conducted in a private setting
 - Only data and/or specimens necessary for the conduct of the study will be collected
 - Data collected (paper and/or electronic) will be maintained in a secure location with appropriate protections such as password protection, encryption, physical security measures (locked files/areas)
 - Specimens collected will be maintained in a secure location with appropriate protections (e.g. locked storage spaces, laboratory areas)
 - Data and specimens will only be shared with individuals who are members of the IRB-approved research team or approved for sharing as described in this IRB protocol
 - Data and/or specimens requiring transportation from one location or electronic space to another will be transported only in a secure manner (e.g. encrypted files, password protection, using chain-of-custody procedures, etc.)
 - All electronic communication with participants will comply with Mass General Brigham secure communication policies
 - Identifiers will be coded or removed as soon as feasible and access to files linking identifiers with coded data or specimens will be limited to the minimal necessary members of the research team required to conduct the research
 - All staff are trained on and will follow the Mass General Brigham policies and procedures for maintaining appropriate confidentiality of research data and specimens
 - The PI will ensure that all staff implement and follow any Research Information Service Office (RISO) requirements for this research
 - Additional privacy and/or confidentiality protections

12. References

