At this time, the study clinician will announce to the subject that the research procedure will begin.

- **A separate description for adults and children if applicable**
Not applicable.
- **The process for obtaining consent from non-English speakers if applicable**
Not applicable.
- **The process to determine capacity to consent and use surrogate decision makers if applicable**

We will conduct the following procedures to determine the capacity to consent:

For subjects with no known diagnosis of mild cognitive impairment or dementia on medical record, we will ask the treating clinicians (if subjects are in the ED or in the hospital) regarding their assessment of capacity to consent and clinical stability to approach the subject. Then, the study clinician will follow the procedures described above to classify the patients based on cognitive impairment status and use the 4-item capacity checklist for consent.

For subjects with a known diagnosis of mild cognitive impairment or mild dementia, we will ask the treating clinicians (if subjects are in the ED or in the hospital) regarding their assessment of capacity to consent and clinical stability to approach the subject. At the same time, we will confirm the availability of a caregiver to serve as a study partner. If caregiver is unavailable, the subject will be excluded. Then, the study clinician will follow the procedures described above to classify the patients based on cognitive impairment status and use the 4-item capacity checklist for consent.

For subjects with a known diagnosis of moderate to advanced dementia, the caregivers will be consented for the study (patients will not be the subjects of our study). We will use the 4-item consent capacity checklist.

- **Procedures to minimize undue influence to enroll, particularly if recruiting the investigators' own patients**
The study team will have no patient/clinician relationship with the potential subjects being approached in this study.

- **Describe post-consent intervention assignment and randomization method if applicable**

We will have three groups of participants based on cognitive ability for this study:

- 1) Patients with normal cognition
- 2) Patients with MCI or mild dementia + their caregivers (both are participants)
- 3) Caregivers of patients with moderate and advanced dementia (only the caregivers are the participants)

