Upon classification of eligible participants into the correct group above, we will randomly assign them into one of two arms of the study using block randomization of four using a computer-generated algorithm:

- 1) Intervention (*ED GOAL*)
- 2) Control (usual care)

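### The written visit steps put the only initial-visit survey after ED GOAL, although the measures table and Section 9 need a pre-intervention baseline

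*Combined protocol and SAP*

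**What the plan says.** Section 5 (Subject Enrollment) covers the delirium screen, cognitive classification and consent, and closes that sequence with "At this time, the study clinician will announce to the subject that the research procedure will begin". Random assignment is described next: "Upon classification of eligible participants into the correct group above, we will randomly assign them into one of two arms of the study". No outcome survey appears in that section.

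Section 6, under Initial enrollment, opens with treatment: "After the consent, our trained study clinician will administer the intervention to the participant in-person, on the phone, or over zoom". The survey step comes second: "After the intervention is completed, the RA will obtain post-enrollment questionnaires and also schedule dates/times for the follow-up appointments". Table 3 lists one assessment for the initial visit, a post-enrollment survey, in the same row as ED GOAL. The paragraph ends with a statement about one arm: "All participants in the intervention arm will receive the same intervention and follow-up procedures". Nothing equivalent is written for controls.

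The measures table later in Section 6 gives the patient and caregiver ACP Engagement surveys the timing "Baseline & at 1, 3, and 6 months". Quality of Communication has the same timing, and Heard and Understood has "Baseline & 1, 3, and 6 months". No row schedules an instrument immediately after ED GOAL.

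Section 9 calls the change in self-reported engagement the primary outcome and compares its mean between arms at one month. It uses baseline again in the within-arm signed-rank test and in the mixed model for missing data. Section 3 labels the design pre/post, and Section 9 sets baseline against a measurement one month after the intervention.

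**The concern.** A change score needs a starting value taken before treatment. The analysis assumes one, but the steps that staff would follow do not produce it. Table 3's four visits (initial, 1, 3 and 6 months) line up with the survey schedule in the measures table (baseline, 1, 3 and 6 months). A research assistant matching the two would naturally treat the post-enrollment survey as the baseline.

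The timing matters because of what the survey measures: "self-reported processes for ACP (knowledge, contemplation, self-efficacy, and readiness), and ACP behavior". Knowledge, contemplation, self-efficacy and readiness are things that a conversation about care goals could shift in the same sitting. A score taken after ED GOAL may already contain part of the effect, in the intervention arm only. The pilot exists to supply preliminary effect sizes for a larger trial (Sections 1 and 9), so a distorted estimate would carry into that planning. A pre-intervention score that was never collected cannot be recovered.

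**Working it through.** The plan gives no figure for an immediate effect of ED GOAL, so there is none to reproduce. The check is a comparison of sections, then one formula.

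**1. Sections side by side**

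| Source | Initial-visit survey | Timing relative to ED GOAL |
|---|---|---|
| Section 5 | none (screening tools only) | not applicable |
| Section 6, Initial enrollment | post-enrollment questionnaires | after |
| Table 3 | post-enrollment survey only | not stated beyond the name |
| Measures table | four surveys at baseline | not stated |
| Sections 3 and 9 | baseline implied | before, by implication |

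The mismatch runs both ways. The baseline surveys have no step, and the post-enrollment survey has no listed content. The screening tools (3D-CAM, MiniCog, QDRS) are not outcome measures.

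**2. Three ways this could play out**

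- Staff collect the surveys before ED GOAL although no step says so: no bias.
- Staff follow Section 6 and the post-enrollment survey serves as baseline: step 3 applies.
- Staff follow Section 6 and the post-enrollment survey is a different instrument: there is no baseline, and the change score cannot be computed.

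**3. The second case**

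Let M be the mean score before treatment in both arms, c the control arm's change to one month, D the true between-arm effect at one month, and fD the effect already present just after ED GOAL. Controls are assumed to be surveyed untreated.

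- Intervention arm: (M + c + D) - (M + fD) = c + (1 - f)D
- Control arm: (M + c) - M = c
- Difference in change: (1 - f)D

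To illustrate, take D = 4.3 - 3.8 = 0.5 points. This is an assumption: the gain comes from a one-arm study, and Section 1 calls it self-efficacy while Section 9 calls it engagement.

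| f (assumed) | (1 - f) x 0.5 |
|---|---|
| 0 | 0.50 |
| 0.25 | 0.375 |
| 0.5 | 0.25 |
| 0.75 | 0.125 |
| 1 | 0 |

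The range of f is open at both ends. If an immediate effect wanes by one month, f exceeds 1 and the estimate changes sign. If scores dip at first, f is negative and the estimate is inflated. If only a share m of the intervention arm is surveyed after ED GOAL, the result is (1 - mf)D; at f = 0.5 this is 0.875D, 0.75D and 0.5D for m = 0.25, 0.5 and 1.

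**4. Which analyses are exposed**

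Exposed: the one-month mean change, the intervention arm's signed-rank test (which would see c + (1 - f)D), and any arm-by-time term in the mixed model, whose terms Section 9 does not give. Not exposed to baseline timing: EMR documentation, the self-reported ACP conversation survey (which has no baseline), and the between-arm comparison of 1-, 3- and 6-month outcomes in the power section.

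**The case against.** The best defense is that a pre-intervention baseline is plainly meant. The measures table lists it, the design is labeled pre/post, and Section 9 contrasts baseline with one month after the intervention. The Section 6 paragraph is also clearly abbreviated. Read literally, it would treat everyone who consents, controls included, and it skips randomization, so its silence about an earlier survey is weak evidence that none takes place. Section 5 answers prompts on screening, consent, capacity and assignment, where an outcome survey would not be expected. The schema is not reproduced in the text available and may show the step.

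Most of this stands. A reader might infer that baseline is wholly undefined, or that the trial uses a post-treatment baseline. The documents support neither: they signal the intent, and nowhere say that the post-enrollment survey is the baseline. But Section 6 answers a prompt for all visits, procedures and data collections, so it is where the step belongs, and the one order it states puts the survey after treatment. If the schema shows an earlier survey, Section 6 and Table 3 still need to match it.

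It is also fair that D, f and m are all assumed. The table above shows the form of the bias and does not predict its size.

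**Conclusion.** The point holds as a conflict between the visit procedures and the rest of the plan, and it should be fixed. Followed as written, Section 6 and Table 3 yield either a post-treatment starting value or none for the change that Section 9 calls primary. In the first case the distortion is the factor (1 - f), which rests on an f the documents do not supply. It is zero if ED GOAL has no immediate effect on scores or if staff survey beforehand anyway.

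Two further inferences go too far. One is that the trial's primary result is compromised as a whole. Section 2 describes a composite primary outcome and the measures table labels four measures primary; two of those four, EMR documentation and self-reported conversations, do not depend on baseline timing. The other is that the follow-up comparisons therefore give an unbiased effect. They are free of this problem only: Section 9 also plans to exclude patients who die before 6 months, which is a separate issue, and survey non-response remains.

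**What to change.** Amend Section 6 and Table 3 so that, in both arms, the baseline ACP Engagement (patient and/or caregiver), Heard and Understood and Quality of Communication surveys are completed after consent and before ED GOAL. Before randomization is better if practical, but collection before ED GOAL is what resolves the conflict. Write out the control arm's initial visit. State what the post-enrollment survey contains, and label any survey kept after ED GOAL as an immediate post-intervention measure that is not used as baseline in the change score, signed-rank test or mixed model.

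If the post-enrollment survey is already the baseline battery, this is a reorder within the visit and costs nothing. Otherwise the initial visit, now about 30 to 60 minutes, becomes somewhat longer, more so for patient-caregiver pairs, who complete two engagement surveys (Table 2). The documents do not give the length of the battery. The 30 to 45 minute follow-up appointments are a poor guide, because they also include as-needed coaching and a survey with no baseline.

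If pre-intervention scores turn out not to exist for the intervention arm, compare one-month scores between arms without using the initial survey in either arm. With equal variances at both times and baseline/one-month correlation r, the variance relative to a properly measured change score is 1/(2(1 - r)): 0.71, 1.00 and 1.67 at assumed r = 0.3, 0.5 and 0.7. Precision is lost only if r exceeds 0.5.
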